8.3. Other Safety Analyses

The analyses of non-laboratory safety test results will be based on GSK Core Data Standards, unless otherwise specified.

The non-laboratory safety test results include:

- ECGs
- Vital signs
- Telemetry and Holter monitoring

Details of the planned displays are presented in Appendix 9: List of Data Displays.

9. PHARMACOKINETIC ANALYSES

The PK analyses described below will be carried out for GSK3358699 and GSK3206944 (acid metabolite) if the latter is quantifiable.

9.1. Endpoint / Variables

9.1.1. Drug Concentration Measures

Refer to Appendix 4: Data Display Standards & Handling Conventions (Section 13.4.3 Reporting Standards for Pharmacokinetic) to generate the plasma GSK3358699 and GSK3206944 concentration-time data, and the intracellular GSK3206944 concentration-time data, after single and repeat doses (Parts A and C), under fasted conditions.

In addition to the intracellular GSK3206944 raw concentration which is measured as ng per mL in reagent, the molar concentration within the monocytes will also be derived (see Appendix 5, Section 13.5.3).

207546

9.1.2. Derived Pharmacokinetic Parameters

Pharmacokinetic parameters will be calculated by standard non-compartmental analysis according to current working practices and using the currently supported version of WinNonlin. All calculations of non-compartmental parameters will be based on actual sampling times.

Pharmacokinetic parameters listed below will be determined from the plasma GSK3358699 and GSK3206944 concentration-time data for Parts A and C, as data permits. Additional parameters may be included as required.

Parameter	Parameter description
AUC(0-t)	 Area under the concentration-time curve from time zero to the time of the last quantifiable concentration (C(t)) Calculated using the linear trapezoidal rule for each incremental trapezoid and the log trapezoidal rule for each decremental trapezoid.
AUC(0-∞)	 Area under the concentration-time curve extrapolated to infinity Calculated as: AUC(0-∞) = AUC(0-t) + C(t) / lambda_z This parameter is calculated for Part A only
AUC(0-24)	 Area under the concentration-time curve from time zero to 24 hours post-dose Using the same method as for AUC(0-t)
AUC(0-tau)	• Area under the concentration-time curve from time zero to the end of the dosing period (dosing interval of duration tau)
Cmax	 Maximum observed concentration Determined directly from the concentration-time data.
tmax	 Time to reach Cmax Determined directly from the concentration-time data.
t1/2(terminal)	 Terminal half-life [The time it takes for the concentration levels to fall to 50% of their value in the terminal phase]. Calculated as: t1/2 = ln(2) / lambda_z Lambda_z is the terminal phase rate constant estimated by linear regression analysis of the log transformed concentration-time data
t1/2(initial)	 Actual initial half-life [The time it takes for the concentration levels to fall to 50% of their value in the initial phase]. Calculated as: t1/2 = ln(2) / lambda_ini Lambda_ini is the initial phase rate constant estimated by linear regression analysis of the log transformed concentration-time data

207546

9.1.3. Summary Measure

In addition to the parameters mentioned above, the following will also be calculated:

Part C	(repeat dose)
R ₀	• Accumulation between 1 single dose (Day 1) and repeat dose (Day 14)
	• Calculated as R0 =AUC(0-tau) Day 14/AUC(0-tau) Day 1
Rs	• Steady state ratio (time invariance kinetics)
	• Calculated as Rs=AUC(0-tau) Day 14/AUC(0-inf) Day 1

9.1.4. Population of Interest

The pharmacokinetic analyses will be based on the Pharmacokinetic population, unless otherwise specified.

9.1.5. Statistical Analyses / Methods

Details of the planned displays are presented in Appendix 9: List of Data Displays and will be based on GSK Data Standards and statistical principles.

Unless otherwise specified, endpoints / variables defined in Section 9.1 will be summarised using descriptive statistics, graphically presented (where appropriate) and listed.

9.1.5.1. **Dose proportionality (Part A)**

Dose proportionality will be assessed for GSK3358699 by visual inspection of:

- Part A (single dose - fasted state): dose normalised AUC(0-∞) [or if not available AUC(0-t)] and Cmax values versus dose.

If data permits, dose proportionality may also be assessed for GSK3358699 using the power model described below.

Dose proportionality (Parts A and C)			
Endpoints			
• Part A (single dose - fasted state): AUC(0-t), AUC(0-∞) and Cmax			
Model specification			
• Power model (log-log linear model):			
$y = \alpha \times dose^{\beta} \iff \log_e(y) = \log_e(\alpha) + \beta \times \log_e(dose)$			
Where			
\circ y = endpoint of interest			
\circ dose = actual dose received under fasted condition			
$\circ \beta$ = parameter associated to dose (slope)			
$\circ \alpha$ = participant-specific random effect (intercept)			
• Terms fitted in the power model:			
• Response: log transformation of the endpoint of interest $\log_e(y)$			

207546

- Fixed continuous covariates: $\log_e(dose)$
- Random: participant
- The Kenward and Roger method for approximating the denominator degrees of freedom and correcting for bias in the estimated variance-covariance of the fixed effects will be used.
- An unstructured covariance structure on the random effects terms (SAS: G matrix, random statement) will be used.

Model checking & diagnostics

- Normality assumptions underlying the model used for analysis will be examined by obtaining a normal probability plot of the residuals and a plot of the residuals versus the fitted values (i.e. checking the normality assumption and constant variance assumption of the model, respectively) to gain confidence that the model assumptions are reasonable.
- If there are any departures from the distributional assumptions, alternative models will be explored using appropriate transformed data.

Model results presentation

Table of the estimated slopes and 90% CI (slope close to 1 implies dose proportionality). The following will be derived:

- Fold-increase for doubling dose: 2^{β} , where β is the slope
- 90% CI for fold-increase: $(2^{b_l}, 2^{b_u})$, where (b_l, b_u) is the 90% CI for the slope

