9.5. Pharmacokinetics

9.5.1. Blood sample collection and analysis

- Blood will be collected into appropriate tubes (type to be confirmed pending ongoing stability investigations) for measurement of GSK3358699 and GSK3206944 concentrations in plasma (approximately 1 mL per time-point up to and including 6 hours post dose and approximately 2 mL per time-point after 6 hours post-dose). **[S1]** and **[S2]**
- Blood (6 mL per time point) will be collected into sodium heparin tubes for the isolation of monocytes and for measurement of GSK3206944 concentrations in monocytes, as specified in the SoA. **[S3]**

- Instructions for the processing, storage and shipping of biological samples will be provided by the sponsor in the SRM. The actual date and time (24-hour clock time) of each sample will be recorded.
- Samples will be used to evaluate the PK of GSK3358699 and GSK3206944 in plasma and GSK3206944 in monocytes. Samples collected for analyses of GSK3358699 and GSK3206944 plasma concentration may also be used to evaluate safety or PD aspects related to concerns arising during or after the study.
- Once the plasma has been analyzed for GSK3358699 and GSK3206944 any remaining plasma will be analyzed qualitatively for other compound-related metabolites and the results reported under a separate protocol. **[E4]**
- Genetic analyses will not be performed on these plasma samples unless consent for this was included in the informed consent. Participant confidentiality will be maintained.

Drug concentration information that may unblind the study will not be reported to the investigator site or blinded personnel until the study has been unblinded.

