10.4.2. Pharmacokinetic Analyses

All PK analyses will be performed on the Pharmacokinetic Population.

Endpoint	Statistical Analysis Methods		
Secondary	Plasma GSK3358699 and the metabolite GSK3206944 concentration- time data will be analysed by non-compartmental methods. Calculations will be based on the actual sampling times recorded during the study. Concentration-time data will be listed for each participant and treatment and summarized by planned time point and treatment.		
	From the plasma concentration-time data, the following pharmacokinetic parameters will be determined, as data permit: maximum observed plasma concentration (C_{max}), time to C_{max} (t_{max}), area under the plasma concentration-time curve [AUC ₍₀₋₂₄₎ , AUC _(0-t) and AUC _(0-∞)], and apparent terminal phase half-life ($t_{1/2}$).		
	PK parameters will be listed for each participant and treatment and summarized descriptively by treatment using the PK population. For each of these parameters, except t_{max} , the following summary statistics will be calculated for the active treatment group at each cohort: median, maximum, minimum, arithmetic mean, 95% confidence interval (CI) for the arithmetic mean, standard deviation, coefficient of variation, geometric mean, 95% confidence interval for the geometric mean and standard deviation of logarithmically transformed data. For t_{max} , median, maximum, minimum, arithmetic mean and standard deviation will be calculated. The first point, last point and number of points used in the determination of lz will be included on the listing of the derived parameters.		

Endpoint	Statistical Analysis Methods			
	Part A: Dose proportionality will be assessed by analysis of log_{e^-} transformed parameters $AUC_{(0-\infty)}$ [or if not available $AUC_{(0-t)}$] and C_{max} using the power model. Further details will be included in the RAP.			
	Part B: A mixed effects model will be fitted on the log _e -transformed parameters $AUC_{(0-\infty)}$ [or if not available $AUC_{(0-t)}$] and C_{max} with fed status as a fixed effect and participant as a random effect. Point estimates and corresponding 90% CIs will be constructed for GSK3358699 fed - GSK3358699 fasted using the residual variance. These will then be back transformed to provide point estimates and corresponding 90% CIs for the geometric mean ratio GSK3358699 fed to GSK3358699 fasted.			

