13.9.7. Pharmacokinetic Tables

Part A

Phar	Pharmacokinetic: Tables							
No.	Population	IDSL / Example Shell	Title	Programming Notes	Deliverable [Priority]			
PK C	oncentration	Data	•	•				
3.1.	РК	PK01	Part A: Summary of Plasma Pharmacokinetic Concentration-time Data by Compound (GSK3358699 or GSK3206944)	By treatment group and compound (GSK3358699 or GSK3206944).	SAC			
3.2.	РК	PK01	Part A: Summary of Intracellular Pharmacokinetic Concentration-time Data	By treatment group.	SAC			
3.3.	РК	PK01	Part A: Summary of Intracellular Molar Concentration Pharmacokinetic Concentration-time Data	By treatment group.	SAC			
PK D	erived Param	eters	·	•				
3.4.	РК	PK06	Part A: Summary of Derived Plasma Pharmacokinetic Parameters (Non-transformed and Log-transformed) by Compound (GSK3358699 or GSK3206944)	By treatment group and compound (GSK3358699 or GSK3206944).	SAC			
Dose	Proportionali	ty						
3.5.	РК	[Non standard] PK_T1	Part A: Summary of Estimated Slope and 90% CI of Dose Proportionality Model	By endpoint (AUC(0-t), AUC(0- ∞), Cmax).	SAC			

Part C	·				
Phar	macokinetic: '	Fables			
No.	Population	IDSL / Example Shell	Title	Programming Notes	Deliverable [Priority]
PK C	oncentration	Data			
3.6.	РК	PK01	Part C: Summary of Plasma Pharmacokinetic Concentration-time Data by Compound (GSK3358699 or GSK3206944)	By treatment group and compound (GSK3358699 or GSK3206944).	SAC
3.7.	РК	PK01	Part C: Summary of Intracellular Pharmacokinetic Concentration-time Data	By treatment group.	SAC
3.8.	РК	PK01	Part C: Summary of Intracellular Molar Concentration Pharmacokinetic Concentration-time Data	By treatment group.	SAC
PK D	erived Param	eters			• •
3.9.	РК	PK06	Part C: Summary of Derived Plasma Pharmacokinetic Parameters (Non-transformed and Log-transformed) by Compound (GSK3358699 or GSK3206944)	By treatment group and compound (GSK3358699 or GSK3206944).	SAC

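### AUC(0-t), whose end point moves with dose, may stand in for a missing AUC(0-inf) in the dose-proportionality assessment; if the assay limit cuts low-dose profiles short, a proportional drug can look more than proportional

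*SAP*

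**What the plan says.** SAP 9.1.2 runs AUC(0-t) only as far as the last concentration the assay can quantify. SAP 9.1.5.1 then gives it two roles in Part A.

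- **Stand-in.** The visual check uses dose-normalised AUC(0-inf), "or if not available AUC(0-t)] and Cmax values versus dose".
- **Endpoint.** The power-model endpoints are "Part A (single dose - fasted state): AUC(0-t), AUC(0-∞) and Cmax", reported by endpoint in Table 3.5, "Part A: Summary of Estimated Slope and 90% CI of Dose Proportionality Model". The model is conditional: "If data permits, dose proportionality may also be assessed for GSK3358699 using the power model described below". Its reading rule is "slope close to 1 implies dose proportionality", with no limits for how close.

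Protocol 10.4.2 goes further. There "Dose proportionality will be assessed by analysis of" log-transformed AUC(0-inf), with AUC(0-t) if that is unavailable, and Cmax in the power model. In the protocol, therefore, the stand-in can enter a slope. The protocol leaves further detail to the RAP.

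Neither document gives an assay limit, a criterion for AUC(0-inf) being unavailable, or a statement on whether substitution is made per profile or for the whole analysis.

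**The concern.** An area that stops at the assay limit covers a different time span at each dose. With a predicted Cmax near 1 ng/ml at 1 mg and a 40-fold dose range, the low-dose curve may drop out of range hours before the high-dose curve. The low doses then contribute a smaller share of their true exposure. Dose-normalised AUC appears to rise with dose, and the log-log slope exceeds 1, because of the assay and not the drug. Mixing the two areas can add to this: AUC(0-inf) is hardest to estimate where few samples are quantifiable, so truncated areas at low doses could sit beside complete ones at high doses. What is at stake is a misreading of a secondary PK result as more than proportional.

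**Working it through.** **Inputs from the documents.** Half-life about 3 h (protocol 5.4). AUC 255 ng/ml.h and Cmax 42 ng/ml at 45 mg (protocol Table 2). Plasma samples at 0.25, 0.5, 1, 2, 4, 6, 8, 12, 24 and 48 h (protocol 2.1). Doses 1, 3, 10, 20, 25, 30 and 40 mg (SAP 5.2). Six active participants per dose, and twelve at 25 mg because both cohorts receive it in Period 4.

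**Assumed.** A one-compartment oral curve, no variability, assay limits from 0.005 to 0.5 ng/ml, and (for the stand-in) AUC(0-inf) treated as unavailable when it has fewer than three post-peak points or needs more than 20% extrapolation.

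**Step 1: reproduce Table 2.** Per mg, AUC = 255/45 = 5.667 and Cmax = 42/45 = 0.933. Multiplying by 1, 3, 10, 20, 35 and 45 mg gives AUC 6, 17, 57, 113, 198, 255 (table: 199 at 35 mg) and Cmax 1, 3, 9, 19, 33, 42 (table: 32 at 35 mg). The protocol's own prediction is proportional to rounding, so the true slope here is 1.

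**Step 2: the curve.** ke = ln 2/3 = 0.231/h. Solving for AUC/Cmax = 255/42 = 6.07 h gives ka = 1.51/h and tmax = 1.46 h. Then

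C(t) = dose × 5.667 × 0.231 × [ka/(ka − ke)] × (e^(−ke·t) − e^(−ka·t)).

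At 1 mg this is 0.097 ng/ml at 12 h and 0.0060 at 24 h. At 40 mg it is 0.24 at 24 h. Any limit between about 0.006 and 0.24 ng/ml ends the 1 mg curve at 12 h or earlier while the 40 mg curve runs to 24 h.

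**Step 3: share of true AUC captured up to time T.** F(T) = 1 − [ka·e^(−ke·T) − ke·e^(−ka·T)]/(ka − ke), so F(4) = 0.532, F(6) = 0.705, F(8) = 0.814, F(12) = 0.926 and F(24) = 0.995.

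**Step 4: slopes.** Regress log AUC on log dose, weighted by n. The mixed column uses AUC(0-inf) where available and AUC(0-t) otherwise.

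| Assumed limit (ng/ml) | Last sample at 1 / 3 / 40 mg (h) | Captured at 1 / 40 mg | AUC(0-t) slope | Mixed slope |
|---|---|---|---|---|
| 0.005 | 24 / 24 / 24 | 99.5% / 99.5% | 1.000 | 1.000 |
| 0.01 | 12 / 24 / 24 | 92.6% / 99.5% | 1.015 | 1.000 |
| 0.05 | 12 / 12 / 24 | 92.6% / 99.5% | 1.024 | 1.000 |
| 0.1 | 8 / 12 / 24 | 81.4% / 99.5% | 1.052 | 1.000 |
| 0.2 | 8 / 12 / 24 | 81.4% / 99.5% | 1.035 | 1.000 |
| 0.25 | 6 / 12 / 12 | 70.5% / 92.6% | 1.058 | 1.074 |
| 0.5 | 4 / 8 / 12 | 53.2% / 92.6% | 1.133 | 1.134 |

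Using linear-up/log-down trapezoids and only the six escalation doses changes little: at 0.5 ng/ml the AUC(0-t) slope is 1.145 and the mixed slope 1.147; at 0.25 the mixed slope is 1.077. The series is not monotone because the last sample can only fall at 4, 6, 8, 12 or 24 h.

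The mixed slope departs from 1 only when the 1 mg profile is substituted. At 0.25 its AUC(0-t) is 29.5% short. At 0.5 it is 46.8% short, with only two quantifiable post-peak points. The 1 and 3 mg doses together carry 69% of the slope's leverage.

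**Step 5: the visual check.** If AUC(0-t) were used for everyone, dose-normalised exposure at 40 mg relative to 1 mg would be 0.995/0.926 = 1.07 at a limit of 0.05, 0.995/0.814 = 1.22 at 0.1, 0.926/0.705 = 1.31 at 0.25 and 0.926/0.532 = 1.74 at 0.5.

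**Step 6: effect on the interval.** In simulations of the six-dose interlocking design (300 trials per setting; assumed between/within log-SDs of 0.30/0.15 and 0.40/0.25), the 90% CI for the AUC(0-t) slope lay wholly above 1 in 17 to 26% of trials at 0.05 ng/ml and 24 to 44% at 0.1, against a nominal 5%. A fixed t multiplier of 1.69 replaced Kenward-Roger, so these figures are indicative.

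**The case against.** The strongest reply is that a reader might infer that the plan will report a proportional drug as more than proportional, and the documents do not support that. No assay limit is stated, and below about 0.006 ng/ml there is no bias at all. Between 0.01 and 0.25 the slope of about 1.02 to 1.06 means 2.02 to 2.08-fold per doubling of dose, against 2.00. That stands, and it makes the point conditional.

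A reader might also infer that the SAP's stand-in sentence distorts a slope. It belongs to the visual inspection, which yields none. In the SAP power model AUC(0-t) replaces nothing: AUC(0-inf) and Cmax appear beside it, so a discrepancy would be visible. Only protocol 10.4.2 puts the stand-in inside a fitted model. This stands too, although the SAP does not say which endpoint to believe if they disagree.

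The power model is optional, there are no formal hypotheses, and the protocol's PK escalation criteria (8.1.7) rest on exposure thresholds and predicted percentiles, not on this slope. That limits the consequence.

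Finally, AUC(0-24) is already planned as a fixed-interval parameter, and AUC(0-t) is a useful check on the extrapolation in AUC(0-inf). Both are fair. AUC(0-24) is not, however, named for proportionality, and where a low-dose profile leaves the assay range before 24 h its value depends on how the unquantifiable part is handled. The second argument favours keeping AUC(0-t) in Table 3.5, but not mixing it with AUC(0-inf).

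**Conclusion.** The concern holds in conditional form. The plan allows an area with a dose-dependent end point to replace AUC(0-inf), and also reports it as a proportionality endpoint without a caution. If the limit truncates low doses earlier, the bias is upward. Its size is nil, small or material depending on an assay limit the documents do not give: AUC(0-t) slope 1.00 up to about 0.006 ng/ml, about 1.02 to 1.06 for 0.01 to 0.25, and about 1.13 to 1.15 at 0.5. Profile-by-profile substitution under the assumed 20% rule does no harm up to 0.2 ng/ml and gives about 1.07 to 1.08 at 0.25 and 1.13 to 1.15 at 0.5. These figures rest on the protocol's predicted exposures and a one-compartment curve; the SAP also plans an initial and a terminal half-life, and a slower terminal phase could make the AUC(0-t) bias larger and affect AUC(0-inf) as well. The consequence is confined to interpreting a secondary PK analysis.

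**What to change.** In SAP 9.1.5.1:

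- Remove the substitution of AUC(0-t) for a missing AUC(0-inf), so the two are never mixed across doses, and record this as a departure from protocol 10.4.2 in SAP 2.1.
- Base the proportionality reading on AUC(0-inf) and Cmax, and state when AUC(0-inf) counts as unavailable.
- Where AUC(0-inf) is missing at some doses, show for all participants an AUC over one common nominal interval as a sensitivity analysis. The interval could end, for example, at the latest nominal time quantifiable in most participants at the lowest dose. Report the share of AUC(0-inf) it covers.
- Keep AUC(0-t) in Table 3.5, labelled supportive, with a note giving the assay limit and its truncating effect.

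The cost is one derived parameter and a few sentences, with no new samples. The common interval omits late exposure, possibly a large share if the limit is high: in the model above it would cover 81% of AUC at a limit of 0.1 ng/ml but only 53% at 0.5. It could also miss non-proportional late elimination, which is why it belongs as a sensitivity analysis.

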10. PHARMACODYNAMIC AND BIOMARKER ANALYSES

10.1. Primary Pharmacodynamic and Biomarker Analyses

The PD parameters collected during the study will be listed for each participant and treatment and summarised descriptively by treatment.

10.1.1. Endpoint / Variables

See Appendix 5: Derived and Transformed Data for the full list of biomarkers and the related displays planned for final SAC.

10.1.2. Summary Measure

Continuous summaries of absolute values, percentage inhibition and predicted percentage inhibition will be presented for each biomarker detailed in Appendix 5, Section 13.5.4.

10.1.3. Population of Interest

These analyses will be based on the Safety population, unless otherwise specified.

207546

10.1.4. Statistical Analyses / Methods

Details of the planned displays are presented in Appendix 9: List of Data Displays and will be based on GSK Data Standards and statistical principles.

Unless otherwise specified, endpoints / variables defined in Section 10.1.1 will be summarised using descriptive statistics, graphically presented (where appropriate) and listed.

11. EXPLORATORY ANALYSES

Exploratory analysis detailed in the protocol will be covered outside of this RAP and reported separately from the main study reporting.

207546

12. **REFERENCES**

GlaxoSmithKline Document Number 2017N332348_05. Study ID 207546: A randomised, double-blind (sponsor open), placebo-controlled, three part study to evaluate the safety, tolerability, pharmacokinetics and pharmacodynamics of single (in both fed and fasted states) or repeat doses of GSK3358699 in healthy male participants. 11-DEC-2018.

13. APPENDICES

13.1. Appendix 1: Schedule of Activities

13.1.1. Part A General Schedule of Activities

Procedure	Screening (up to 35 Days prior to Day 1)					Т		ent Pe ay 1	eriod	1-3			Day 2	Day 3	Treatmen	Follow-up 1 (7-14 days post-last dose)	Follow-up 2 (5 dose ±	Notes
Flocedule	35 Days prior to / 1)	Day -1	Pre-dose	0 h	15 mins	30 mins	1 h	2 h	4 h	6 h	4 8	12 h	24 h	48 h	Treatment Period 4	4 days post-last se)	5 weeks after last : 3 days)	The 2nd follow up visit is only required for those participants where challenges are being administered and blisters induced i.e. treatment period 4
General																		
Informed consent	Х														S			
Inclusion and exclusion criteria	x	x													See separate Period 4 S			Day -1 assessment is to recheck eligibility against medical conditions, prior therapy etc, but not against Day - 1 clinical chemistry and haematology results (see Section 9.4.7 of Protocol GlaxoSmithKline Document Number 2017N332348_05).
Demography	Х														ichec			
Medical/medication/drug/ alcohol history	x	x													Schedule of Activities			Includes substance usage and family history of premature cardiovascular (CV) disease and current medical conditions.
Admission to unit for in-patient stay		х													ties			

Procedure	Screening (up to 35 Days prior to Day 1)					Tı	reatm Da	ent Pe ıy 1	eriod 1	1-3			Day 2	Day 3	Treatment Period 4	Follow-up 1 (7-14 days post-last dose)	Follow-up 2 (5 w dose ± 3	Notes
	5 Days prior to 1)	Day -1	Pre-dose	0 h	15 mins	30 mins	1 h	2 h	4 h	6 h	8 h	12 h	24 h	48 h	Period 4	days post-last ²)	5 weeks after last 3 days)	The 2nd follow up visit is only required for those participants where challenges are being administered and blisters induced i.e. treatment period 4
Discharge from Unit following in- patient stay	_													Х				
Outpatient visit	Х															Х	Х	
Safety Assessments including la	aborato	ry tes	ts					1										
Full Physical Exam	Х																	
Brief Physical Exam		Х												X	S	Х		
Vital Signs	x	x	x					x	x		x	x	x	x	See separate Period 4 Schedule of Activities	х	x	Blood pressure (BP), heart rate (HR), temperature, respiratory rate. See Section 9.4.4 of Protocol GlaxoSmithKline Document Number 2017N332348_05 for details on triplicate and single measurement timepoints.
12-Lead ECGs	x	x	x					x	x		x	X	x	x	Schedule of Activities	X		12 Lead ECGs will be performed in triplicate at screening, Day-1, Day 1 pre-dose, Day 2 and Day 3. Single ECGs will be performed at other time points and if any cardiac symptoms are experienced. ECGs to be performed prior to blood draws and dosing where these fall at the same nominal time.

	Screening					Т	reatm	ent Pe	eriod 1	-3			1	1	Trea	Follow-up 1	Follow-up 2 (dose	Notes
Procedure	(up to 3 Day						Da	ay 1					Day 2	Day 3	atment	1 (7-14 dose	+ 25	
	Screening (up to 35 Days prior to Day 1)	Day -1	Pre-dose	0 h	15 mins	30 mins	1 h	2 h	4 h	6 h	8 h	12 h	24 h	48 h	Treatment Period 4	(7-14 days post-last dose)	5 weeks after last 3 days)	The 2nd follow up visit is only required for those participants where challenges are being administered and blisters induced i.e. treatment period 4
Telemetry			<=:	=====	====	=====	====: :	=====	===== :>	====	====:		===					from 1 h pre-dose to 24 h post-dose
Holter monitoring (24 hours)	Х																	If a participant is rescreened the Holter will not need to be repeated.
HIV, Hep B, Hep C	Х																	
Haematology	x	x									x		x	x		х		Fasted screening samples. 24 and 48 hour samples will be taken prior to participants receiving breakfast
Coagulation	х										х		x	x		х		Fasted screening samples. 24 and 48 hour samples will be taken prior to participants receiving breakfast
Clinical Chemistry	x	x									х		х	х		х		Fasted screening samples. 24 and 48 hour samples will be taken prior to participants
Urinalysis	х	х									х		x	х		х		Fasted screening samples. 24 and 48 hour samples will be taken prior to participants receiving breakfast
Drug / Alcohol Test	Х	Х																
Urine Cotinine	Х	Х																
Visual forearm check (cosmetic assessment or blister healing where appropriate)	x	x														х	x	Visual forearm checks are only required if participant is scheduled to take part in treatment period 4. Details of checks:

Screening (up to 35 Days prior to Day 1) Follow-up 1 (7-14 days post-last dose) Follow-up 2 (5 weeks after last dose ± 3 days) **Treatment Period 1-3** Notes Ireatment Period 4 Day 3 Day 2 Day 1 Procedure Day -1 The 2nd follow up visit is only required Pre-dose for those participants where 15 mins 30 mins 24 h 48 h 0 h ́а h 12 h 4 8 2 h 4 h 6 h challenges are being administered and blisters induced i.e. treatment period 4 Screening check prior to first • treatment period (cosmetic assessment) Day -1 check in treatment ٠ Period 3 only. Between Day -1 and Day 2 (ie 48 hour window) (cosmetic assessment) Period 4 (cosmetic ٠ assessment and blister healing). For further detail on time points in Period 4 see Section 13.1.1.1. Follow-up visits 1 and 2 ٠ (blister healing) SAEs collected from signing of informed consent form until the final follow up visit; AEs collected AE / SAE review continuously from time of first dose until the final follow up visit Monitored from first dose until the end of the final treatment Period **Concomitant Medication Review**

Procedure	Screening (up to 35 Days prior to Day 1)					Т		ent Pe ay 1	eriod 1	-3			Day 2	Day 3	Treatment Period 4	Follow-up 1 (7-14 days post-last dose)	Follow-up 2 (5 v dose ±	Notes
	35 Days prior to (1)	Day -1	Pre-dose	0 h	15 mins	30 mins	1 h	2 h	4 h	6 h	8 h	12 h	24 h	48 h	Period 4	4 days post-last e)	$e \pm 3$ days)	The 2nd follow up visit is only required for those participants where challenges are being administered and blisters induced i.e. treatment period 4
Treatment Administration																		
Study Drug / Placebo Administration				x											See Period 4 SoA			
Pharmacokinetics, Pharmacody	namics	and C	Genet	ics Sa	ample	S							•					
Blood sampling for systemic PK [S1] and [S2]			x		х	x	x	x	x	Х	Х	х	x	x	Se			
Blood sampling for intracellular PK [S3]							Х		Х		Х		х	Х	e sepai			
Blood sample for ex vivo PD assay [S4]		x	x				x		x		х	x	x	x	See separate Period 4 Schedule of Activities			Six samples (3 LPS and 3 null) are required on Day -1: to be taken (LPS and null) at approximately 13:00, 17:00 and 20:00. Day 1: Two pre-dose samples (LPS and null) to be taken at approximately 08:00.
Blood sample for circulating proteins [E1a]			Х					Х	Х		Х		х		dule of			
Blood sample for gene panel [E1b]			Х					Х	Х		Х		Х		Activit			
Blood sample for companion diagnostic development		X													ies			Sample to be taken on Day -1 in treatment Period 1 only.

Procedure	Screening (up to 35 Day 1)					T		ent Pe iy 1	eriod 1	-3			Day 2	Day 3	Treatment Period	Follow-up 1 (7-14 d dose)	Follow-up 2(5 w dose ± (Notes
	35 Days prior to 1)	Day -1	Pre-dose	0 h	15 mins	30 mins	1 h	2 h	4 h	6 h	8 h	12 h	24 h	48 h	Period 4	4 days post-last e)	5 weeks after last 3 days)	The 2nd follow up visit is only required for those participants where challenges are being administered and blisters induced i.e. treatment period 4
Genetics sample for CES genotyping and optional genetic research [E5]		x																Sample to be taken on Day -1 in treatment Period 1 only.
Urine sample for metabolite analysis [E4]			x	<==					=====									Pre-dose sample, immediately prior to dosing participants will be instructed to void their bladder into a collection container. Following dosing participants will be instructed to collect all urine voided for a 0-24 hour collection.

